**CONFIDENTIAL**

## Appendix B – PD Inpatient Clinical Knowledge and Management Study (PICK)

### Education Plan Overview

Prior to launch of the educational plan, there will be Nursing Grand Rounds. The curriculum will also be introduced to case managers, pharmacists, physical and occupational therapists and dieticians. Clinical Level III and IV registered nurses on each unit will be designated with the responsibility of steering the education on the unit. They will be directly supported by Nurse Educators and the Department of Neurosurgery clinicians.

The educational plan will be rolled out by direct testing, education and retesting to each nursing unit with distribution via print material and electronic material. Contact hours will be awarded for those completing the pre-test, webinar and post-test.

**Step 1:** Administration of a Parkinson's disease knowledge base assessment test to the target audience via HOLA.

**Step 2:** Introduction of the PD webinar through HOLA. During this step, there will also be posters and other educational material available to the units.

**Step 3:** Re-administer the Parkinson's disease knowledge base assessment test to determine retention.

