## **Primary Objective**

To measure the difference in knowledge of the clinicians before and after completing the Parkinson's Disease Inpatient Clinical Knowledge and Management Program.

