## **Primary Endpoints**

Difference in PD Knowledge assessment score before and after Parkinson's Disease Inpatient Clinical Knowledge and Management Program (Appendix A- PD Knowledge assessment score).

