### **Knowledge Assessment Methodology**

1. Administer Parkinson's Disease (PD) Pre-test to target audience via HOLA (HackensackUMC Online Learning Academy) Learning Management System. Time frame for completion: 4 weeks.
2. Administer PD Webinar to target audience via HOLA followed by Post-test. Time frame for completion: 4 weeks.

3. Administer a follow-up Post-test to target audience via HOLA 4 months after completion of PD webinar. (Time Frame for completion: 4 weeks)
4. Award contact hours to those completing the pre-test, webinar and post-test.
5. Develop educational poster on PD to display on all in-patient nursing units.
6. Coordinate Nursing Grand Rounds on Parkinson's Disease to include contact hours.
7. Additional Educational Resources:
  - a. PD Nurse Champions
  - b. Unit Based Council Chairs
  - c. PD Best Practice Alert - EPIC

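### Appendix B places Nursing Grand Rounds on Parkinson's disease before the baseline knowledge test, so the 'before' score of the primary endpoint may already include teaching

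*Combined protocol and SAP*

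**What the plan says.** The Primary Objective is "To measure the difference in knowledge of the clinicians before and after completing the Parkinson's Disease Inpatient Clinical Knowledge and Management Program". The Primary Endpoints section makes this a score difference on the 20-item test in Appendix A.

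Appendix B describes how the test and the teaching are delivered, in two places.

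- **Education Plan Overview.** On Grand Rounds and the other disciplines: "Prior to launch of the educational plan, there will be Nursing Grand Rounds. The curriculum will also be introduced to case managers, pharmacists, physical and" (the list goes on to occupational therapists and dietitians). On the plan itself: "The educational plan will be rolled out by direct testing, education and retesting to each nursing unit". Its Step 1 is "Administration of a Parkinson's disease knowledge base assessment test to the target audience via HOLA". The webinar, posters and other materials come in Step 2, and the retest in Step 3.
- **Knowledge Assessment Methodology.** Item 1 is the pre-test, with four weeks to complete it. Item 2 is the webinar and post-test, and item 3 is a further post-test four months later. Item 6 is "Coordinate Nursing Grand Rounds on Parkinson's Disease to include contact hours", with no date.

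Neither place requires the pre-test to be finished before Grand Rounds, or before other disciplines meet the curriculum. Neither says who attends Grand Rounds, what they cover beyond the disease itself, or whether attendance before the pre-test is recorded.

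**The concern.** The knowledge comparison has no concurrent control group. The pre-test score is the only reference against which the Program is judged. Anything on the test that clinicians learn before taking it raises that reference and is subtracted from the measured gain.

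A site that follows the Overview would hold an accredited session on Parkinson's disease first and take the 'before' score second. The Data Analysis section makes no provision for earlier exposure. Once a clinician has attended, a clean baseline for that person cannot be recovered. At stake is an understated effect on the primary endpoint and a greater chance of retaining Ho1 wrongly. The plan gives no significance level, power, effect size or standard deviation, so nobody can say how much understatement it could absorb.

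**Working it through.** **Order of events**

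1. The Overview puts Grand Rounds before launch of the educational plan.
2. It defines that plan as testing, then education, then retesting, with the knowledge test as Step 1. The pre-test is therefore inside the plan and follows its launch.
3. Together these give: Grand Rounds, launch, pre-test.
4. The sentence on the other disciplines has no time of its own. The word 'also', straight after the Grand Rounds sentence, suggests the same pre-launch slot but does not state it.
5. In the Methodology list, items 1 to 3 carry time frames and items 4 to 7 do not. If the list is chronological, Grand Rounds fall after the four-month post-test, which contradicts the Overview. If it is not, it says nothing on their timing. Either way it does not show that the pre-test comes first.

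**Content.** Grand Rounds content is not described. The learning objectives in Appendix B, which apply to the educational offerings in general, include pathophysiology, contraindicated drugs and timely dosing. Appendix A tests these: item 4 (neurotransmitter), items 7, 16 and 20 (contraindicated or safe drugs), items 14, 18 and 19 (timing and delay). Overlap is likely but not documented. This reads the two mentions of Grand Rounds as the same activity.

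**Who could be exposed** (Sample Size Calculation, Table 1)

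- Plan's own total: 100 + 87 + 48 + 19 + 40 + 17 + 12 + 17 + 6 = 346. This reproduces the stated figure.
- Nursing roles: staff nurses 100 + advanced practice nurses 87 + nurse educators 19 = 206; 206/346 = 59.5%.
- Other disciplines named in the Overview: case managers 48 + dietitians 17 + pharmacists 12 + physical therapists 17 + occupational therapists 6 = 100; 100/346 = 28.9%.
- Both together: 306/346 = 88.4%. The 40 physician's assistants (11.6%) are named in neither sentence.

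These shares are ceilings for the roles concerned. They are not attendance figures.

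**Possible attenuation.** Let *s* be the share eligible for early exposure, *a* the fraction of these who attend before their pre-test, and *r* the fraction of the full gain they acquire there. If the full gain is the same in all roles and the post-test score does not depend on when the material was learnt, then

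measured gain / full gain = 1 − *s* × *a* × *r*.

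The documents give neither *a* nor *r*. Assumed ranges: *a* from 10% to 100%, *r* from 10% to 50%.

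| Eligible | *a* = 10%, *r* = 10% | *a* = 50%, *r* = 25% | *a* = 100%, *r* = 50% |
|---|---|---|---|
| Nursing roles (*s* = 0.595) | 99.4% | 92.6% | 70.2% |
| Nursing plus named disciplines (*s* = 0.884) | 99.1% | 88.9% | 55.8% |

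The extremes of the second row are 1 − 0.884 × 0.10 × 0.10 = 0.991 and 1 − 0.884 × 1 × 0.50 = 0.558.

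**The case against.** The best defence is that Appendix B is loosely drafted and the intent is clear. The Methodology is the operational list and begins with the pre-test. The Sample Size Calculation section also speaks of clinicians before and after the education program is implemented. This shows intent, but it does not remove the Overview's explicit statement that Grand Rounds come first. The Overview holds posters and other materials back to Step 2, after the pre-test, and gives Grand Rounds no such place.

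A second defence concerns what is being estimated. The objective does not say that Grand Rounds are part of the Program. If the Program is only the webinar with its tests, the difference is a valid gain from the knowledge level at launch, and there is no bias. This stands as a condition on the conclusion. The plan would then need to say so, because its result would describe a narrower intervention.

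Three stronger readings are tempting, and the documents do not support them.

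- A reader might infer that the other disciplines are certainly taught the curriculum before baseline. The timing is inferred from one word, and 'introduced' may mean announced.
- A reader might infer a definite, large loss. For example, an assumed full gain of 4 of 20 items, with 1 to 2 learnt early by all 306, gives a loss of 22–44%. No item gain is stated anywhere, and low attendance would make the loss under 1%.
- A reader might infer that comparisons between roles are spoiled. No objective or endpoint compares roles.

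**Conclusion.** The point holds as a sequencing defect with a plausible effect on the primary endpoint. It does not show that the baseline has in fact been taught. As the Overview is written, Grand Rounds on Parkinson's disease precede the pre-test. The curriculum introduction may precede it too, and the Methodology list does not settle either.

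The likely direction is toward no difference, provided that Grand Rounds count as part of the Program and cover tested content. Such a bias would not create a false gain. Its size is open: under the assumed ranges, between 99% and 56% of the full gain would be measured if all 306 clinicians are eligible, and between 99% and 70% if only the nursing roles are. Confidence is moderate, because attendance, content and the timing of the curriculum introduction are all unstated. The correction is worth making because it protects the only comparator of the primary endpoint at almost no cost.

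**What to change.** 1. Amend Appendix B so that the HOLA pre-test opens and closes before Nursing Grand Rounds and before any curriculum content is introduced to any discipline.
2. Make the Education Plan Overview and the Knowledge Assessment Methodology give the same dated order, and state whether Grand Rounds are a component of the Program.
3. If sessions have already been held, use the contact-hour roster and each clinician's pre-test date to flag those who attended first. Report the primary difference with and without them. This assumes that such a roster was kept, which the plan does not confirm. Attenders may also differ from the rest, so this comparison is a sensitivity check and does not restore a clean baseline.

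Cost: Grand Rounds move by about four weeks, the length of the pre-test window. No extra tests or staff are needed.

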## **Hypothesis**

Ho1:

Parkinson's Disease Inpatient Clinical Knowledge and Management Program will not make a difference in the clinician knowledge.

Ha1:

Parkinson's Disease Inpatient Clinical Knowledge and Management Program will make a difference in the clinician knowledge.

Parkinson's Disease Inpatient Clinical Knowledge and Management Program will not make a difference in the customized PD order time and PD medication administration time, complications (administered contraindicated medication, falls, positive delirium scores, and positive confusion), medication error and length of stay during hospitalization.

Ha2:

Parkinson's Disease Inpatient Clinical Knowledge and Management Program will make a difference in the customized PD order time and PD medication administration time, complications (administered contraindicated medication, falls, positive delirium scores, and positive confusion), medication error and length of stay during hospitalization.

Ho3:

WatchRx System will not make a difference in the customized PD order time and PD medication administration time, complications (administered contraindicated medication, falls, positive delirium scores, and positive confusion), medication error and length of stay during hospitalization.

Ha3:

WatchRx System will make a difference in the customized PD order time and PD medication administration time, complications (administered contraindicated medication, falls, positive

delirium scores, and positive confusion), medication error and length of stay during hospitalization.

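### The primary endpoint measures change between sittings of one 20-item test with no comparison for retesting, so rejecting Ho1 cannot be read as an effect of the Program alone

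*Combined protocol and SAP*

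**What the plan says.** The Hypothesis section states Ho1 causally: "Parkinson's Disease Inpatient Clinical Knowledge and Management Program will not make a difference in the clinician knowledge". Primary Endpoints defines the outcome as "Difference in PD Knowledge assessment score before and after Parkinson's Disease Inpatient Clinical Knowledge and Management Program" and points to Appendix A, which holds one set of 20 items. Primary Objective asks only for a before/after difference.

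Appendix B sets out the sequence. Education Plan Overview says "The educational plan will be rolled out by direct testing, education and retesting to each nursing unit", and its last step is "Re-administer the Parkinson's disease knowledge base assessment test to determine retention". Knowledge Assessment Methodology starts with a pre-test through the online learning system, allowing 4 weeks. It continues with "Administer PD Webinar to target audience via HOLA followed by Post-test", allowing another 4 weeks, and then "Administer a follow-up Post-test to target audience via HOLA 4 months after completion of PD webinar".

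Sample Size Calculation counts about 346 clinicians before and after the education. Neither it nor Appendix B mentions an alternate form, an untaught or wait-list group, or clinicians who are only retested. Data Analysis names two-sided tests for independent groups, names no paired test, and has no adjustment for retesting. Limitations lists only single site and convenience sample.

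**The concern.** A test of zero mean change between two sittings has as its null that scores do not change between sittings. That is the same as Ho1 only if having met the items adds nothing to later scores. The plan neither states that assumption nor collects data that could check it. Clinicians may recognise an item at the second sitting, or may have looked it up or discussed it during the testing windows.

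As written, the plan would report any such gain as a difference made by the Program. At stake is what the primary result may claim: a significant rise could come from teaching, from prior exposure to the questions, or from both, and the design cannot separate them.

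**Working it through.** **The plan's own figure.** The sample column of Table 1 gives 100 + 87 + 48 + 19 + 40 + 17 + 12 + 17 + 6 = 346, which matches the stated number. It is a head count; the plan gives no alpha, power or effect size to reproduce.

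**Assumptions, none of them in the documents.** Two-sided alpha 0.05; score SD 2, 3 or 4 items out of 20; correlation between sittings 0.5 (varied from 0.3 to 0.7); Program effect zero; retest gain g = 0.5 item (also 1 item).

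**Paired test.** SD of change = SD × √(2(1 − 0.5)) = SD. The noncentrality is g√n / SD of change, with √346 = 18.60. For SD 3 it is 0.5 × 18.60 / 3 = 3.10. Against a critical value of 1.967, the rejection probability is about Φ(3.10 − 1.967) = 87.1%. The smallest mean gain that reaches significance is 1.967 × SD / 18.60.

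**Unlinked independent groups, 346 per sitting.** The standard error is SD × √(2/346) = 0.0760 × SD. For SD 3 it is 0.228, so 0.5 / 0.228 = 2.19 and rejection is about Φ(2.19 − 1.96) = 59.2%.

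| Score SD | Smallest significant gain, paired | Rejection at 0.5 item, paired | Rejection at 0.5 item, unlinked groups |
|---|---|---|---|
| 2 | 0.21 | 99.6% | 90.8% |
| 3 | 0.32 | 87.1% | 59.2% |
| 4 | 0.42 | 64.0% | 37.6% |

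**Sensitivity.**
- Over correlations 0.3 to 0.7 and SD 2 to 4, the paired test rejects in 50% to 100% of trials at half an item and in at least 97.5% at one item.
- The unlinked test rejects in at least 90.8% at one item.
- If the same people sit twice (correlation 0.5) but the independent-groups test is applied, half an item rejects in 97.0%, 62.9% and 32.8% for SD 2, 3 and 4.
- With 173 paired completers (half of 346), half an item rejects in 90.5%, 58.7% and 37.3%.

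**Check that the missing comparison is the cause.** In 20,000 simulated trials with SD of change 3, a half-item retest gain and no Program effect, the single-group test rejected in 87.4%. When the change scores of 173 clinicians were compared with those of 173 who were only retested, rejection was 4.7%. With no retest gain, the single-group test held 5.1%.

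**The case against.** The strongest reply is that testing belongs to the Program. Education Plan Overview puts testing and retesting inside the rollout, and contact hours depend on completing the pre-test, webinar and post-test. A clinician who looks up an item after the pre-test is then responding to the Program. Primary Objective and Primary Endpoints ask only for a before/after difference, and the study calls itself observational and quasi-experimental. On this view only the wording of Ho1 goes too far.

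Much of this stands. The mismatch is with Ho1/Ha1 and the research question, not with the objective or endpoint. But the documents nowhere say that learning from the test itself, still less recognition of an item, counts as the Program's effect. If that is intended, Ho1 has to say so.

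Other limits also stand:
- The sizes above describe how sensitive the test is; they are not evidence that a retest gain exists. A reader might infer that any small gain will reject Ho1. It need not: at half an item the probability falls to about 38% with unlinked groups and SD 4.
- A reader might assume that every clinician is linked across sittings. The documents do not say so, and partial completion is foreseeable.
- A reader might infer that a true effect is overstated by the whole retest gain. That assumes the two gains add, yet an item learned both by look-up and from teaching scores once.

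**Conclusion.** The concern holds as a limit on the primary conclusion. Under a paired or an unpaired analysis, the endpoint tests for no change between sittings of the same items, and the plan has nothing to separate a retest gain from a Program effect. The size is conditional on the assumed SD, correlation, alpha, retest gain and completion. With 346 clinicians, a half-item gain alone rejects in about 64% to 99.6% of trials paired (correlation 0.5) and about 38% to 91% unlinked.

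A reader might go further and infer that the Program teaches nothing, or that a positive result would be false. The documents do not support that: a retest gain does not exclude a real effect. Nor do they show that the primary endpoint must be replaced. The before/after change answers the stated objective, provided it is described as what it is.

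**What to change.** Reword Ho1/Ha1 and the primary conclusion as *change in Appendix A score between the pre-test and post-test sittings, including any effect of retesting and of the other rollout components*. Do not report rejection as an effect of the webinar or the Program alone. Add the uncontrolled same-item retest to Limitations. This costs a few lines of text and needs no new data.

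Optional, only if the pre-test has not been run: randomise in the learning system which half of the items each clinician sees at pre-test, and give all 20 at post-test. As a supportive analysis, compare post-test scores on unseen items with pre-test scores on the other half, averaged equally over the two randomised halves. Balance the halves for content. An odd/even split would put overlapping topics on both sides, for example contraindicated or safe drugs in item 07 against items 16 and 20.

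This needs two pre-test item sets but no extra clinicians or sittings. Its costs:
- **Precision.** In an item-level simulation under assumed item behaviour, the standard error rose from about 0.14 to 0.20 items (0.20 / 0.14 = 1.43, about 40%). The gain detectable with 80% power moved from about 0.40 to 0.57 items.
- **Item sharing between colleagues.** With a retest gain of 0.71 items and no Program effect, assumed leakage of 25% or 50% leaves a bias of 0.18 or 0.36 items. False rejection is then about Φ(0.18 / 0.20 − 1.96) = 14% or Φ(0.36 / 0.20 − 1.96) = 43%, using unrounded biases, against about 5% with no leakage.
- **Permission.** The instrument is adopted with permission, and dividing it may need the owner's agreement.

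These costs are why the contrast is proposed as supportive and not as the primary endpoint.

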### **Knowledge Assessment Methodology**

1. Administer Parkinson's Disease (PD) Pre-test to target audience via HOLA (HackensackUMC Online Learning Academy) Learning Management System. Time frame for completion: 4 weeks.
2. Administer PD Webinar to target audience via HOLA followed by Post-test. Time frame for completion: 4 weeks.

3. Administer a follow-up Post-test to target audience via HOLA 4 months after completion of PD webinar. (Time Frame for completion: 4 weeks)
4. Award contact hours to those completing the pre-test, webinar and post-test.
5. Develop educational poster on PD to display on all in-patient nursing units.
6. Coordinate Nursing Grand Rounds on Parkinson's Disease to include contact hours.
7. Additional Educational Resources:
  - a. PD Nurse Champions
  - b. Unit Based Council Chairs
  - c. PD Best Practice Alert - EPIC

## **Objectives:**

After participating in educational offerings, the (HackensackUMC employed) target audience will be able to:

1. Describe the pathophysiology of Parkinson's Disease (PD).
2. Discuss the signs and symptoms of PD.
3. Identify the treatment options and medications used to manage patients with PD.
4. Explain the medication contraindications for patients with PD.
5. Explain the importance of administration of PD medications "On Time Every Time."
6. Recognize the complications of not giving PD medications on time

## **Target Audience:**

1. Advanced Practice Nurses
2. Physician's Assistant (PA)
3. In-patient registered nurses practicing on:
  - a. Medical/Surgical units

- b. Critical Care units/PACU
- c. Emergency & Trauma Center
- d. Surgical Admission Suite (SAS)
- e. Center for Ambulatory Surgery (CAS).

- 4. Case Managers
- 5. Pharmacists
- 6. Dietitians
- 7. Physical Therapist
- 8. Occupational Therapist

## **Appendix C – Aware in Care Kit**

A kit containing useful tools and information for helping PD patients during their hospital visits. Includes the following:

- Parkinson's Disease ID Wrist Bracelet
- Medical Alert Card
- Medication Form
- PD Fact Sheet

### **PD ID Wrist Bracelet**

Designation to be worn at all times in the event of emergency situations and for hospital tracking purposes.

### **Medical Alert Card**

Includes emergency information.

### **Medication Form**

Includes information regarding prescriptions, existing medication regimen and scheduling, and other patient information.

### **PD Fact sheet**

Information to be shared with hospital staff and included in patient chart.

## Appendix E – Educational Information on PD Medication

THIS PATIENT HAS PARKINSON'S DISEASE		
To Avoid Serious Side Effects Please Make Sure Parkinson's Medications are given		
ON TIME, EVERY TIME!		
(Within 30 Minutes)		
COMMON PD MEDS	CONTRAINDICATED MEDICATIONS	
Sinemet (Carbidopa/Levodopa)	Prochlorperazine (Compazine) Cyclobenzaprine (Flexeril)*	
Selegiline (Eldepryl)	Promethazine (Phenergan) Tramadol (Ultram)*	
Rasagiline (Azilect)	Metoclopramide (Reglan) Haloperidol (Haldol)	
Amantadine (Symmetrel)	Meperidine (Demerol) Fluphenazine (Prolixin)	
Comtan (Entacapone)	Methadone * Chlorpromazine (Thorazine)	
Requip (Ropinirole)	Droperidol	
Mirapex (Pramipexole)	* If on Selegiline or Rasagiline	
Stalevo (Carb/Levo/Entacapone)		

